7.2. Secondary Endpoints and the Analytical Methods

7.2.1. Secondary Endpoints and the Analytical Methods

Analysis set: Full Analysis Set

Analysis items:

Sleep latency by actigraphy

Total nocturnal sleep time by actigraphy

Nocturnal wake time by actigraphy

Number of nocturnal awakenings by actigraphy

Sleep efficiency by actigraphy

Total nocturnal sleep time by sleep diary

Number of nocturnal awakenings by sleep diary

Daytime activity level by actigraphy (steps)

Time Point: Baseline, Week 4, Week 8, End of the treatment period

Analysis Methods: For the above analysis items, the same analyses as described in 7.1.1. will be performed for secondary endpoints.

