5.2.2 Secondary endpoints

- Change in diary-measured sleep latency* from baseline to the end of the treatment period
- Change in actigraphy-measured total nocturnal sleep time* from baseline to the end of the treatment period
- Change in actigraphy-measured nocturnal wake time* from baseline to the end of the treatment period
- Change in actigraphy-measured number of nocturnal awakenings* from baseline to the end of the treatment period
- Change in actigraphy-measured sleep efficiency* from baseline to the end of the treatment period
- Change in diary-measured total nocturnal sleep time* from baseline to the end of the treatment period
- Change in diary-measured number of nocturnal awakenings* from baseline to the end of the treatment period
- Change in actigraphy-measured daytime activity level* from baseline to the end of the treatment period

*: Mean value from the past 7 days

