13.1.3 Efficacy analysis

[Primary endpoint]

Change in actigraphy-measured sleep latency* from baseline (i.e., start of the study treatment period) to the end of the treatment period

*: Mean value from the past 7 days

[Analytical methods]

In the Full Analysis Set, the change in actigraphy-measured sleep latency from baseline to the end of the treatment period will be summarized by calculation of summary statistics (i.e., number of participants, mean, standard deviation, maximum, minimum, and quartiles; hereinafter the same) and a two-sided 95% confidence interval for the mean, and assessed using the one-sample *t*-test.

[Secondary endpoints]

- Change in sleep diary-measured sleep latency* from baseline to the end of the treatment period
- Change in actigraphy-measured total nocturnal sleep time* from baseline to the end of the treatment period

- Change in actigraphy-measured nocturnal wake time* from baseline to the end of the treatment period
- Change in actigraphy-measured number of nocturnal awakenings* from baseline to the end of the treatment period
- Change in actigraphy-measured sleep efficiency* from baseline to the end of the treatment period
- Change in sleep diary-measured total nocturnal sleep time* from baseline to the end of the treatment period
- Change in sleep diary-measured number of nocturnal awakenings* from baseline to the end of the treatment period
- Change in actigraphy-measured daytime activity level* from baseline to the end of the treatment period

*: Mean value from the past 7 days

[Analytical methods]

In the Full Analysis Set, the individual secondary endpoints will be summarized by calculation of summary statistics and two-sided 95% confidence interval for the mean, and assessed using the one sample *t*-test.

[Other endpoints]

- Actigraphy-measured sleep latency, total nocturnal sleep time, nocturnal wake time, number of nocturnal awakenings, sleep efficiency, and daytime activity level
- Diary-measured sleep latency, total nocturnal sleep time, and number of nocturnal awakenings
- PGI
- HAM-D17
- 3DSS

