7. EFFICACY EVALUATIONS

7.1. Primary Endpoint and the Analytical Methods

7.1.1. Change from Baseline in Sleep Latency by Actigraphy

Analysis set: Full Analysis Set

Analysis items: Sleep latency by actigraphy

Time point: Baseline, Week 4, Week 8, End of the treatment period

Analysis methods: For the above analysis items, the following analysis will be performed.

- (1) As the analyses for primary endpoint, summary statistics and two-sided 95% confidence interval (CI) of the mean will be calculated for both change and percentage change from baseline to the end of treatment period, and one sample t-test will be conducted to assess the change within a subject. The same analyses as described above will be performed for change and percentage change at Week 4 and Week 8. In addition, mean plots with +/- SD for change and percentage change will be displayed at each time point.
- (2) For change and percentage change from baseline to each time point, case plots will be illustrated at each time point.
- (3) For observed value at each time point, case plots will be displayed, and summary statistics and two-sided 95% CI of the mean will be calculated. Mean plots with +/- SD will be also displayed at each time point.

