7.3.4. Correlation between Endpoints

Analysis set: Full Analysis Set

Analysis items: Sleep latency by actigraphy

Sleep latency by sleep diary

Total nocturnal sleep time by actigraphy

Total nocturnal sleep time by sleep diary

Time Point: End of the treatment period

Analysis Methods: Correlation charts between the items below will be illustrated and Spearman’s correlation coefficient will be calculated.

Sleep latency by actigraphy vs. sleep diary

Total nocturnal sleep time by actigraphy vs. sleep diary

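### SAP 7.2.1 lists the primary variable where the protocol's first secondary endpoint, change in diary sleep latency, belongs, so the SAP never tests that endpoint

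*SAP*

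**What the plan says.** Protocol 5.2.2 opens its list of eight secondary endpoints with "Change in diary-measured sleep latency* from baseline to the end of the treatment period". Protocol 13.1.3 repeats it, again in first place: "Change in sleep diary-measured sleep latency* from baseline to the end of the treatment period". The method there applies to every item on the list: "the individual secondary endpoints will be summarized by calculation of summary statistics and two-sided 95% confidence interval for the mean, and assessed using" (a one-sample t-test is then named). Both protocol versions in the file agree on this.

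SAP 7.1.1 covers the primary endpoint, with "Analysis items: Sleep latency by actigraphy". It specifies summary statistics and a two-sided 95% interval for change and percentage change, and states that "one sample t-test will be conducted to assess the change within a subject".

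SAP 7.2.1 then lists eight items for the secondary analyses, beginning with "Sleep latency by actigraphy". Its method sentence reads "For the above analysis items, the same analyses as described in 7.1.1. will be performed for secondary endpoints". That sentence reaches only the variables listed above it, and diary sleep latency is not among them.

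**The concern.** The SAP is the document from which the outputs are programmed, and protocol 13.1 relies on it for endpoint definitions and methods covering all study objectives. If 7.2.1 is followed literally, the primary variable is analysed a second time by the same method, and the first-listed secondary endpoint has no change estimate, interval or test.

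This endpoint measures the same quantity as the primary, from the patient's side. Protocol 6.2 supports the choice of measures by citing a guideline that recommends patient sleep logs for subjective evaluation in addition to objective measurement. With no control arm and no blinding, readers will want to see whether actigraphy and diary latency move together. If the change analysis is added only after results are known, it may look post hoc. If it is never added, a prespecified endpoint goes unreported.

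**Working it through.** There is no stated figure to reproduce; the check is a comparison of lists, followed by a search of the SAP for any other analysis of the missing item.

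**Step 1. The two lists side by side**

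| Slot | Protocol 5.2.2 and 13.1.3 | SAP 7.2.1 | Match |
|---|---|---|---|
| 1 | Sleep latency, diary | Sleep latency, actigraphy | No |
| 2 | Total nocturnal sleep time, actigraphy | Same | Yes |
| 3 | Nocturnal wake time, actigraphy | Same | Yes |
| 4 | Number of awakenings, actigraphy | Same | Yes |
| 5 | Sleep efficiency, actigraphy | Same | Yes |
| 6 | Total nocturnal sleep time, diary | Same | Yes |
| 7 | Number of awakenings, diary | Same | Yes |
| 8 | Daytime activity, actigraphy | Same | Yes |

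Seven of eight match. One protocol endpoint is absent (1/8 = 12.5%), and one SAP item duplicates the primary.

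**Step 2. Every other place where the SAP deals with diary sleep latency**

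- Section 2: the time-window rules for diary data. No analysis.
- Section 5: a term in the derivation of diary total sleep time, and a maximum-minus-minimum daily variation. No analysis of latency change.
- 6.2.1: baseline description only.
- 7.3.4: a chart and Spearman coefficient for "Sleep latency by actigraphy vs. sleep diary" at the end of treatment only. A cross-sectional rank correlation says nothing about change; it can be high when diary latency has not moved.
- Section 9: the sleep diary data listing.

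None of these gives a change from baseline, an interval or a test.

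**Step 3. Counting what is missing**

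- Against the protocol: one estimate (change from baseline to end of treatment) with its interval and t-test. The protocol plans 1 primary + 8 secondary = 9 end-of-treatment change tests. The SAP covers 8 distinct variables.
- Against the SAP's scheme in 7.1.1(1): 2 scales (change, percentage change) × 3 time points (Week 4, Week 8, end of treatment) = 6 estimates per variable. Across 7.1.1 and 7.2.1 the nominal count is 6 × (1 + 8) = 54 tests, of which 6 × 8 = 48 are distinct because actigraphy latency occurs twice. With the item corrected, 6 × 9 = 54 are distinct.

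**Step 4. Slip or decision?**

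The baseline list in SAP 6.2.1 gives actigraphy latency and then the eight protocol secondary variables in protocol order, with diary latency first among them. SAP 7.2.1 keeps that count and order but has actigraphy where the diary belongs. The revision-history entry for 7.2.1 records additions only and no removed endpoint. This points to a clerical slip, although the documents do not state the cause.

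**The case against.** The discrepancy itself is hard to dispute. The case against concerns its weight.

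- **The protocol still prescribes the test.** This stands: the two documents conflict, and the endpoint has not been withdrawn. The statement that it is never tested applies to the SAP as written.
- **Six missing estimates overstates the protocol's commitment.** This also stands. Week 4, Week 8 and percentage change come from the SAP, and percentage change was added only in version 2.0. For a participant with Week 8 data, the end-of-treatment value will normally be the Week 8 value, so the six are not six separate results. The loss against the protocol is one estimate.
- **Other subjective measures survive.** True: diary total sleep time (derived by subtracting diary latency), diary awakenings, the HAM-D17 sleep items, the 3DSS quality score and PGI are all still analysed. None gives the change in diary sleep latency.
- **A diary is itself open to expectation effects in an open-label study.** Fair; it cannot validate the actigraphy result. That bears on interpretation and does not justify leaving out a prespecified endpoint.
- **The study is exploratory, with 30 participants, no power calculation and no multiplicity adjustment, and the primary analysis is untouched.** All correct, and repeating the primary causes no bias. These points limit the harm, but the endpoint still has no planned change analysis.

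**Conclusion.** The concern holds. As written, the SAP contains no change estimate, confidence interval or t-test for the protocol's first secondary endpoint, and it lists the primary variable a second time in that position. The size is one of eight secondary endpoints (12.5%): one protocol-specified estimate, or six under the SAP's own scheme. The primary analysis, the 5% two-sided level and the sample size are unaffected.

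The conclusion rests only on the wording of the two documents and needs no numerical assumption. That the cause was clerical is an inference from the list order and the revision history, and the conclusion does not depend on it. The correction is needed because a prespecified endpoint otherwise has no planned result.

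**What to change.** In SAP 7.2.1, replace the first item with sleep latency by sleep diary, the label already used in 6.2.1 and 7.3.4, and keep actigraphy sleep latency in 7.1.1 only. The list then agrees with the protocol on all eight items, and the existing cross-reference to 7.1.1 supplies the method. Record the change in SAP section 11 as a correction that restores the protocol endpoint, with its date, so that it cannot be read as a post hoc addition.

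The cost is one line of SAP text, one revision entry and one set of diary-latency outputs in place of the repeated primary outputs. Diary latency is already collected under protocol 9.1.8 and already used in the SAP's derivations. No change to data collection, significance level or sample size is needed.

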7.3. Other Analyses

7.3.1. Patient Global Impression of Improvement (PGI)

Analysis set: Full Analysis Set

Analysis items: PGI [Very much worse, Much worse, A little worse, No change, A little improved, Much improved, Very much improved]

Time Point: End of the treatment period

Analysis Methods: For the above analysis items, the following analysis will be performed

- (1) The number of subjects and the percentage will be calculated for each category.

7.3.2. Hamilton Rating Scale for Depression-17 (HAM-D17)

Analysis set: Full Analysis Set

Analysis items:

01. Depressed mood (Sadness, hopeless, helpless, worthless)	[0, 1, 2, 3, 4]
02. Work and activities	[0, 1, 2, 3, 4]
03. Genital symptoms	[0, 1, 2]
04. Somatic symptoms gastrointestinal	[0, 1, 2]
05. Loss of weight (Rated by A or B)	
A. Rating by history	[0, 1, 2, 3]
B. Rating weekly by measuring weight by ward psychiatrist	[0, 1, 2, 3]
06. Insomnia early	[0, 1, 2]
07. Insomnia middle	[0, 1, 2]
08. Insomnia late	[0, 1, 2]
09. Somatic symptoms general	[0, 1, 2]
10. Feelings of guilt	[0, 1, 2, 3, 4]
11. Suicide	[0, 1, 2, 3, 4]
12. Anxiety psychic	[0, 1, 2, 3, 4]
13. Anxiety somatic	[0, 1, 2, 3, 4]
14. Hypochondriasis	[0, 1, 2, 3, 4]

15. Insight	[0, 1, 2]
16. Retardation (Slowness of thought and speech, impaired ability to concentrate, decreased motor activity)	[0, 1, 2, 3, 4]
17. Agitation	[0, 1, 2, 3, 4]
HAM-D17 total score	[0<=<8, 8<=<17, 17<=<24, 24<=]
HAM-D17 total score (except for sleep related score)	
HAM-D17 total score (sleep related score)	

Time Point: Baseline, Week 4, Week 8, End of the treatment period

Analysis Methods: For the above analysis items, the following analysis will be performed

- (1) The number of subjects and the percentage will be calculated for each category.
- (2) For HAM-D17 total score, HAM-D17 total score (except for sleep related) and HAM-D17 total score (sleep related), summary statistics will be calculated and case plots will be displayed.
- (3) For HAM-D17 total score, HAM-D17 total score (sleep related) and HAM-D17 total score (except for sleep related), summary statistics and two-sided 95% CI of the mean will be calculated for both change and percentage change from baseline to each time point, and one sample t-test will be conducted to assess the change within a subject.

7.3.3. 3 Dimensional Sleep Scale (3DSS)

Analysis set: Full Analysis Set

Analysis items:

01. I sleep for less than 6 hours on weekdays.
02. I cannot get enough sleep even though I want to.
03. I go to bed at a fixed, regular time on weekdays and weekends.
04. I wake up at a fixed, regular time on weekdays and weekends.
05. I have a well-balanced breakfast every day.
06. It takes me more than 30 minutes to fall asleep.
07. I wake up more than twice a night.
08. I wake up earlier than usual (for over 2 hours), and cannot fall asleep again.
09. I don't sleep soundly.
10. I worry that I cannot fall asleep.
11. I don't feel free from sleepiness or fatigue when I wake up.

12. I feel sleepy not only in the afternoon, but also in the morning and/or evening.

13. I often doze off.

14. “Morningness” is better suited to me than “Eveningness”.

[Strongly Agree, Agree, Disagree, Strongly Disagree] for the question 1 - 14.

15. What time do you wake up on weekdays?

[6 A.M. or earlier, Around 6:30 A.M., Around 7 A.M., Later than 7 A.M.]

Phase scale score

Quality scale score

Quantity scale score

Time Point: Baseline, Week 4, Week 8, End of the treatment period

Analysis Methods: For the above analysis items, the following analysis will be performed

- (1) The number of subjects and the percentage will be calculated for each category.
- (2) For phase scale score, quality scale score and quantity scale score, summary statistics will be calculated and case plots will be displayed.
- (3) For phase scale score, quality scale score and quantity scale score, summary statistics and two-sided 95% CI of the mean will be calculated for both change and percentage change from baseline to each time point, and one sample t-test will be conducted to assess the change within a subject.

7.3.4. Correlation between Endpoints

Analysis set: Full Analysis Set

Analysis items: Sleep latency by actigraphy

Sleep latency by sleep diary

Total nocturnal sleep time by actigraphy

Total nocturnal sleep time by sleep diary

Time Point: End of the treatment period

Analysis Methods: Correlation charts between the items below will be illustrated and Spearman’s correlation coefficient will be calculated.

Sleep latency by actigraphy vs. sleep diary

Total nocturnal sleep time by actigraphy vs. sleep diary

8. SAFETY EVALUATION

8.1. Evaluation of Adverse Event

8.1.1. Brief Summary of TEAE

Analysis set: Full Analysis Set

Analysis items: TEAE

Category Classification:

Causal relationship with study drug [related, unrelated]

Severity [Mild, Moderate, Severe]

Date of onset [1<= - <29, 29<= - <58, 58<= - <=Max]

For the above analysis items, the following analyses will be performed.

(1) Brief summary of TEAE

- 1) All TEAEs
- 2) TEAEs related to study drug
- 3) TEAEs by severity
- 4) TEAEs related to study drug by severity
- 5) TEAEs leading to study drug discontinuation
- 6) Serious TEAEs
- 7) Serious TEAEs related to study drug
- 8) Serious TEAEs leading to study drug discontinuation
- 9) TEAEs leading to death
- 10) TEAEs by date of onset

Incidence rates will be calculated based on the following rules.

[Frequency of Subjects]

In case of the analysis by severity, subjects with one or more adverse events within a level of MedDRA term is counted only once in that level using the most severe incident. The denominator when calculating the incidence of adverse events is the number of subjects of Full Analysis Set.

In case of the analysis by date of onset, subjects with one or more adverse events are counted once in each category of period when the incident occurred. The denominator when calculating the incidence of adverse events is the number of subjects who are administrated the study drug on and after the period, or the subjects with TEAEs on and after the period. The numerator is the number of subjects with TEAEs on the period.

In the analyses other than the above, subjects with one or more adverse events within a level of MedDRA term is counted only once in that level. The denominator when calculating the incidence of adverse events is the number of subjects of Full Analysis Set.

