6.0 STUDY DESIGN

6.1 Study Design

(1) Study design

This is a multicenter, open-label study.

(2) Treatment

Participants will take ramelteon 8 mg once daily orally at bedtime for 8 weeks.

(3) Planned sample size

30 patients

(4) Number of study sites

Approximately 5 medical institutions

(5) Duration of evaluation and number of visits in individual participants

The duration of evaluation in this study will be 9 weeks. Participants will make a total 4 visits, i.e., at the start of the run-in period and at the start and Weeks 4 and 8 of the treatment period.

Figure 6.a shows the schematic diagram of the study design. The study schedule is provided in Appendix A.

[figure not shown]

Figure 6.a Schematic of Study Design

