8.0 TREATMENT

8.1 Study Drug

8.1.1 Study drug

Nonproprietary name: Ramelteon [JAN]

Chemical name: N-{2-[(8S)-1,6,7,8-Tetrahydro-2H-indeno[5,4-b]furan-8-yl]ethyl}
propanamide

Dosage: 8 mg once daily

Method of administration: Orally at bedtime

Duration of treatment: 8 weeks

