2. TIME WINDOW

[Actigraphy, Sleep diary]

Since the response data of actigraphy and sleep diary at each time point are the mean of data which collected in the previous 7 days, a set of data before each time point will be evaluated if they meet in the time window. For example, if a set of data belongs to the both time windows at week 4 and week 8, a set of data will be divided into two groups, which are for Week 4 and Week 8.

When there are two or more sets of data in the same time window, the one with the nearest visit date to the reference date will be selected, and if the time differences from the reference date are the same, the later data will be adopted.

Assessment time point	Reference Date	Time window
		Days after the first administration
At the start of the treatment period (baseline)	Day 1	Day -7 to Day 1
Week 4 of the treatment period	Day 29	Day 2 to Day 32
Week 8 of the treatment period	Day 57	Day 33 to Day 60
At the end of the treatment period	The latest set of the data group during the treatment period	Day 2 to Day 60

The day before the first day of the administration will be referred to as Day -1, and the first day of administration as Day 1.

[PGI, HAM-D17, 3DSS, Weight]

When there are two or more data in the same time window, the one with the nearest assessment date to the reference date will be selected, and if the time differences from the reference date are the same, the later data will be adopted.

Assessment time point	Reference Date	Time window
		Days after the first administration
At the start of the treatment period (baseline)	Day 1	Day -7 to Day 1
Week 4 of the treatment period	Day 29	Day 2 to Day 32
Week 8 of the treatment period	Day 57	Day 33 to Day 60
At the end of the treatment period	The latest day during the treatment period	Day 2 to Day 60

The day before the first day of the administration will be referred to as Day -1, and the first day of administration as Day 1.

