6.3.2. Study Drug Exposure

Analysis set: All subjects who are given at least one dose of the study drug.

Analysis Items:

Duration of study drug exposure (days) [$1 \leq - < 29$, $29 \leq - < 58$, $58 \leq - \leq \text{Max}$]

Analysis Methods: For the above analysis items, the following analysis will be performed.

- (1) The number of subjects and the percentage will be calculated for discrete variables, and summary statistics will be calculated for continuous variables.

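### The denominator for adverse events by day of onset admits off-drug subjects only if they had an event, so the class from Day 58 is undefined or 100% on schedule; the effect is confined to descriptive safety tables

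*SAP*

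**What the plan says.** SAP 8.1.1 groups TEAEs by onset day into three classes: "Date of onset [1<= - <29, 29<= - <58, 58<= - <=Max". In whole days these are 1–28, 29–57, and 58 onward. The denominator for each class starts from "the number of subjects who are administrated the study drug on and after the period". A second clause then widens it to take in further people by their outcome: "or the subjects with TEAEs on and after the period". On the other side of the fraction, the SAP states: "The numerator is the number of subjects with TEAEs on the period". SAP 8.1.2 repeats the classes by system organ class and preferred term and refers back to 8.1.1 for the counting rules. The other TEAE tables divide by the Full Analysis Set.

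The protocol sets the length of treatment: "Participants will take ramelteon 8 mg once daily orally at bedtime for 8 weeks" (Protocol 6.1), and likewise "Duration of treatment: 8 weeks" (Protocol 8.1.1). SAP 2 treats "the first day of administration as Day 1", sets the Week 8 reference at Day 57 and accepts Week 8 data up to Day 60. Protocol 10.2.1.1 ends adverse-event collection when the treatment period is completed or discontinued. The TEAE definition in SAP 5 has no upper day limit.

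SAP 6.3.2 applies the same three cuts to "Duration of study drug exposure (days", which SAP 5 computes as last dose date minus first dose date plus 1.

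**The concern.** Entry to an incidence denominator should not depend on the outcome. Under this rule, a subject who has stopped the drug and has an event in the period adds one to both numerator and denominator. A subject who has stopped, is equally observed and has no event is left out. The rule bites hardest where few subjects are still being dosed, and the last class begins after the planned last dose. A reader of the safety section could meet a late-onset rate of 100% that reflects only how the cell was built.

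The exposure table inherits the same cut. A subject who took every planned dose shares a class with one who stopped at about half-way, so the classes do not show what an exposure table is usually read for.

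**Working it through.** The plan gives no adverse-event rate to reproduce, so the check is on the day arithmetic and the formula.

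**Days.** With the first dose on Day 1, the reference day for week w is 1 + 7w. Week 4 gives 1 + 28 = 29 and Week 8 gives 1 + 56 = 57, both as in SAP 2. Eight weeks of daily dosing is 8 × 7 = 56 doses, so the planned last dose is on Day 56. The first cut (29) is 28 + 1; the second (58) is 56 + 2.

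**Formula.** Let D be the subjects dosed in the period or later, a those among D with an event in the period, and k the subjects with an event in the period who were not dosed in it or later. Under the SAP rule, when no other subject enters through a later event, incidence = (a + k)/(D + k). Each subject counted in k raises it unless it is already 100%.

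**Last class (Day 58 onward), on schedule.** D = 0 and a = 0. With no event the cell is 0/0. With one event it is 1/1 = 100%, and with two it is 2/2 = 100%. Divided by the planned 30 subjects, one event would be 1/30 = 3.3%.

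**Last class with some late dosing.** D is assumed, because the documents do not give it; a = 0 and k = 1.

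| D (assumed) | SAP rule | Incidence |
|---|---|---|
| 1 | 1/2 | 50% |
| 3 | 1/4 | 25% |
| 5 | 1/6 | 16.7% |
| 10 | 1/11 | 9.1% |

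**Middle class (Days 29–57).** Assume that 27 of 30 subjects are dosed on or after Day 29, and that 2 of the 27 have events: 2/27 = 7.4%. Now let some of the three earlier stoppers have a recorded event in Days 29–57.

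| Stoppers with an event | SAP rule | Full Analysis Set of 30 |
|---|---|---|
| 1 | 3/28 = 10.7% | 3/30 = 10.0% |
| 2 | 4/29 = 13.8% | 4/30 = 13.3% |
| 3 | 5/30 = 16.7% | 5/30 = 16.7% |

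In this example the SAP rule stays within one percentage point of the Full Analysis Set rate. The rule also admits subjects whose only event comes later. If 1 to 3 stoppers have an event only on or after Day 58, the middle-class rate falls slightly, from 2/28 = 7.1% to 2/30 = 6.7%.

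**Exposure.** A last dose on Day 56 gives 56 − 1 + 1 = 56 days, or 57 if a dose is also taken on the visit day. Both fall in 29–57, as does a subject who stopped on Day 29 (29 days). Moving the cut from 58 to 57 would still leave the 56-day completer in the middle class.

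**The case against.** The defence has force on several points.

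- Because adverse-event collection ends with the treatment period, the last class should usually be empty or nearly so. Few subjects can be off drug and still observed. This stands, and it limits how often the problem will show.
- The event clause keeps the numerator inside the denominator, and it changes nothing for a subject dosed in the period or later. That is a fair purpose, but counting everyone under observation serves it without selecting on outcome.
- The Day 58 cut keeps the scheduled Day 57 visit in the Week 8 class, with Day 58 onward as overflow. This also stands: a 57-onward class would push events on the scheduled visit day into the overflow.

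Stronger readings are tempting, and the documents do not support them. A reader might infer that the number of completers is hidden, so that the safety and primary results cannot be read. But SAP 6.1.3.1 tabulates completion with reasons for non-completion, SAP 6.3.2 also gives summary statistics for exposure, and SAP 9 lists end-of-study status and adverse events. No primary analysis uses these classes. A reader might also infer that completers are pooled with all early stoppers, but those who stopped by Day 28 have their own class. Nor can a specific bias be stated, such as 100% against a true 20%. That would need counts of late visits and late events that the documents do not give.

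**Conclusion.** The point holds as a minor defect in a stated rule. The by-onset denominator selects off-drug subjects on the outcome. On schedule the class from Day 58 can yield only an undefined value or 100%; with an assumed 1 to 10 subjects dosed late, one off-drug event gives 50% down to 9.1%. The middle class is also affected, but in the example its rate stays close to the Full Analysis Set figure.

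An actual 100% needs two things: a recorded event on or after Day 58, and no event-free subject dosed on or after that day. The first depends on collection running on to a late final visit, which the documents neither state nor rule out.

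The consequence is limited to the onset tables in SAP 8.1.1 and 8.1.2. Overall TEAE incidence and the primary endpoint are unchanged. The exposure classes in SAP 6.3.2 are a weakness of display, and no information is lost.

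**What to change.** - **SAP 8.1.1 and 8.1.2, denominator.** Use all subjects still under adverse-event observation at the start of the period, whether or not they are on drug and whether or not they have an event. The simpler alternative is the Full Analysis Set, as in the other TEAE tables.
- **SAP 8.1.1 and 8.1.2, classes.** Keep the scheduled Day 57 visit inside the Week 8 onset class. Either merge Day 58 onward into it or show that class as counts without a percentage.
- **SAP 6.3.2.** Add an upper exposure class that starts slightly below 56 days, with the cut chosen to fit the tolerance allowed around the final visit. The SAP's Week 8 data window opens at Day 33, too early to supply that cut, so the value needs its own statement.

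The cost is a change of SAP wording and minor reprogramming of three outputs (SAP 6.3.2, 8.1.1 and 8.1.2). No new data are needed, although the observation-based denominator requires an end-of-observation date for each subject; the Full Analysis Set option avoids that.
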